This issue of dry beriberi has got less attention and in our extensive literature search we have failed to identify any document related to dry beriberi in this part of Bangladesh. So, it is rational to design a prospective study to determine the clinical pattern of patients with suspected dry beriberi and their outcome to thiamine therapeutic challenge in our setting. Our study result is likely to sensitize the health professionals of this region about this neglected health issue by increasing awareness of the clinical spectrum of TD. Moreover, study may provide the impetus for fashioning national policies on the diagnosis, treatment and prevention of thiamine deficiency disorders in our country.

5. Metarials and methods:

5.1 Type of study: Quasi-experimental study, self –controlled clinical trial (pretest – posttest design)

5.2. Period of study: One year.

5.3. Place of study: Department of Neurology, Department of Medicine of Chittagong Medical College Hospital.

5.4. Study population: All the patients admitted in the above mentioned ward of CMCH with clinical diagnosis of suspected dry beriberi.

5.5. Sampling technique: Required number of patients will be selected purposively as per set criteria

5.6. Eligibility criteria:

Inclusion criteria:

1. Any person admitted to CMCH as a Suspected/Possible dry-beriberi.

Risk factors + at least 2 of the following signs:

Risk factors include Imbalanced diet (diet poor in thiamine/rich in carbohydrate or anti-thiamine factors), malnutrition, alcoholism, GIT surgery, chronic diarrhoea, chronic vomiting, pregnancy or history of recent delivery, chronic. diuretics use, renal dialysis, total parenteral nutrition.

- a) Muscle weakness of upper and or lower limb (less than grade 5 power in MRC scale)
- b) Positive sensory symptoms (burning, tingling or pain)
- c) Objective sensory deficit (pain, touch, position, vibration sense)
- d) Absent or reduced deep tendon reflexes
- e) Positive squat test (unable to rise after squatting without help)
- f) Leg swelling

2. Age 18 years and above

Exclusion criteria:

1. Patients with isolated cardiac/wet beriberi
2. Patient with known causes of peripheral neuropathy such as Diabetic, hereditary, Demyelinating (GBS, CIDP), metabolic (hepatic/renal impairment), drugs (e.g. INH, Ethambutol, Phenytoin, Metronidazole, Dapsone etc.) Toxin (As ,OPC, Pb ,Hg except alcohol) etc.
3. Patients refuse to participate

5.7. Sample size:

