To estimate the prevalence following formula will be used to determine the sample size by doing finite population correction:

$$n = \frac{z^2 pqN}{d^2 \times (N - 1) + z^2 pq}$$

Where,

n= required sample size,

z= z-value of standard normal distribution at a given level of significance

p=prevalence of the event (Prevalence of clinically suspected dry beriberi patients show positive response to thiamine trial, usually from previous study)

q=100-p

d= allowable error/precision in the estimate of 'p'= usually 10% of p

N= Expected number of suspected dry-beriberi patients admitted in Neurology and Medicine department of CMCH during data collection period.

Here,

$z= 1.96$ at 95% confidence level

$p=80\% = 0.8$ [Prevalence of clinically suspected dry beriberi patients show positive response to thiamine trial is not available from extensive literature search. However, from our experience, 80% of these patients show positive response].

$q= (100-80)\% = 20\% = 0.2$

$d=10\% \text{ of } p = .1 \times .7 = .07$

$N= 75$

$$\text{So, } n = \frac{1.96^2 \times 0.8 \times 0.2 \times 75}{(.08)^2 \times (75-1) + 1.96^2 \times 0.8 \times 0.2} = 41.6 \approx 42$$

However, final sample size will be increased to 55 assuming 30% drop out.

5.8. Data collection tool:

- A predesigned Case Record Form.

5.9. Procedure of collecting data:

All patients attending the above mentioned ward with a diagnosis of suspected dry beriberi will be assessed for eligibility. Informed written consent will be obtained from the patients or attendants after full explanation of the ultimate outcome, complications and purpose of the study. They will be informed of their right to withdraw from the study at any stage. After consenting, the details of the patient's history including demographic information, food habit, clinical findings at presentation, results of laboratory, and neuroimaging testing will be recorded in case record form. A general physical examination (e.g. pulse, blood pressure, respiratory rate), neurological examination (higher mental function, cranial nerves, Motor, sensory, cerebellar function), results of laboratory and electro-diagnostic testing (if necessary) were recorded in case record form. Then therapeutic trial of Inj. Thiamine is given IV for 1st week (200mg IV daily) then orally (tab. Thiamin 100mg bd) for 12 weeks. Patients will be followed up after 1, 6 and 12 week to see the response.

5.10. Data analysis:

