All the data will be checked and edited after collection. Continuous data will be reported as the means \pm SD or median and itraquartile range. Qualitative or categorical data will be described as frequencies and proportions. Proportions will be compared using chi-square or Fisher's exact test whichever will be applicable. To determine whether any of the difference between pretreatment and post treatment values were statistically significant or not, either Friedman's test or Cochran's Q test were used. Former test compares the quantitative variables and non-dichotomous qualitative variables and the later test compares the dichotomous qualitative/categorical variables. Statistical significance will be defined as $P < 0.05$ and confidence interval will be set at 95% level. SPSS (Statistical Package for Social Science) for Windows version 23 software will be used for the analyses.

5.11. Variables under study:

Primary Outcome Variable:

1. Treatment response measured by Overall Neuropathy Limitation Scale (ONLS) score before and after treatment.

Secondary Outcome Variables:

1. Comparison and Assessment of clinical features at presentation and after treatment: leg swelling, muscle cramp, muscle power (MRC grading), deep tendon reflexes, sensory impairments (tingling /burning /pain/ touch/ position /vibration), squat test.

5.12 Operational definition:

Risk factors: Imbalanced diet (diet poor in thiamine/rich in anti-thiamine factors), malnutrition, alcoholism, GIT surgery, chronic diarrhea, chronic vomiting ,pregnancy, diuretics, renal dialysis, total parenteral nutrition.

Anti-Thiamine factors: Raw or fermented fish,shell fish,ferns, Tea, coffee, betel nuts

Possible/suspected dry beriberi: Risk factors + at least 2 of the following signs:

- a) Muscle weakness of upper and or lower limb (less than grade 5 power in MRC scale)
- b) Positive sensory symptoms (burning, tingling or pain)
- c) Objective sensory deficit (pain, touch, position, vibration sense)
- d) Absent or reduced deep tendon reflexes
- e) Positive squat test (unable to rise after squatting without help)
- f) Leg swelling

Probable dry beriberi: Above symptoms recovered after thiamine treatment.

Socio-economic status: It will be measured as per Modified Kuppuswamy Socio-economic scale (Appendix-A) and grouped into five categories :Upper class, Upper middle class, Lower middle class, Upper lower class and Lower class.

5.14. Utilization of results:

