19. Frank LL. Thiamine in clinical practice. *JPEN J Parenter Enteral Nutr* (2015) 39(5):503–20. doi:10.1177/0148607114565245 10

PART –E

BUDGET

I. Total Budget: 2,50,000 bdt (Two lacs and fifty thousand taka only)

II. Detailed Budget:

1. Personnel cost: Not Applicable.
2. Field Expenses/ Laboratory Costs: 1,50,000.
3. Supplies and Materials:
4. Patient Cost (if applicable): Transport fee 55,000.
5. Travel cost (Internal travel cost only) : 5000.
6. Transportation of Goods: Not Applicable.
7. Office Stationary: Internet 5000
 Stationary 5000
 Photocopy 5000.
8. Data Processing/ Computer Charges: 15,000.
9. Printing and Reproduction: 10,000.
10. Contractual Services (other than manpower): Not Applicable.
11. Administrative Overhead: Not Applicable.
12. Miscellaneous: Not Applicable.

PART-G

CASE RECORD FORM

Title: Efficacy of Thiamine in Patients with Clinically Suspected Dry Beriberi: An Open Labeled Hospital Based Study.

ID no: **Ward No:** **Bed no:** **Reg. No:**

Date of admission: **Date of Discharge:**

Date of inclusion in study:

Contact No: **Address:**

Particulars of the Patient:

1. Name:
2. Age (in years):
3. Sex: Male=1/Female=2.
4. Religion: Muslim=1/ Hindu=2/Buddist=3 / Christian=3
5. Marital Status: Married=1/ Unmarried=2/ widow=3/divorced=4.
6. Residence: urban=1/ semi urban=2/rural=3/others=4(specify).
7. Education:
8. Occupation:
9. Monthly Income:
10. Food Habit:
 - a) Rice eaten: Polished un-boiled=1/polished boiled=2
 - b) Washing before cooking:times
 - c) Discarding excess water after cooking: no=1/yes=2.
 - d) No of meals per day:

e) Contents of major meals:

Breakfast	Snacks	Lunch	Afternoon Snacks	Dinner

f) Anti-thiamine food intake: Betel nut/ tea/ fermented fish/shell fish.

.....min after major meal,.....times per day

11. Alcohol intake:

Duration.....years, Amount:...../day

current alcohol user=1/ former alcohol user=2/ never alcohol user=3.

12. Other associated conditions (if any):

GIT surgery/ Chr. Diarrhoea/ Chr. Vomitting/Renal disease/ cancer/ pregnancy/others (specify):

13. No of childbirth (in females):

Time of last childbirth:

Duration of Lactation:

12. Presenting Symptoms:

12.1) Limb Weakness: Upper limb/ lower limb/ both. Duration:.....days

12.2) Leg swelling: yes/ no. Duration.....days

Nil=0, Mild=+, moderate=++, severe=+++

12.3) Sensory Impairment (pain, tingling, numbness): yes/ no. Duration: Days.

12.4) anorexia , nausea : yes/ no. Duration: Days.

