12.5) Muscle cramp: no/mild/moderate/severe. Duration: Days.

12.6) other symptoms (specify): Duration: Days.

13. Physical Examination:

13.1) Height:, weight:.....Kg, BMI (weight/height²):

13.2) Mid Upper Arm Circumference(MUAC):.....cm

13.3) Anaemia: Absent/ Present.

13.4) muscle power (MMRC Grading):

Upper Limb	Lower Limb
Proximal:	Proximal:
Distal:	Distal:

13.5) deep tendon reflexes: normal =0, Diminished=1, Absent=2

	Biceps	Triceps	Supinator	Knee	Ankle	Planter
Right						
Left						

[figure not shown]
13.6) Squat test: negative=0/ positive=1.

13.7) Sensory Impairment: Normal =0, Diminished=1,Absent=2

	pain	touch	temperature	Position sense	vibration
Upper limb					
Lower limb					

13.8) neuropathic Pain (VAS Score):
nil=0/mild=1/moderate=2/sever=3.

13.8) Pulse :/min

13.9) BP:m m hg

13.10) Resp Rate:/min

13.11) JVP: normal/ Raised

13.12) other :if present,(specify)

14. Investigations:

14.1) CBC:

14.2) Urine R/E:

14.3) Serum creatinine:

14.4 Serum Electrolytes:

14.5) LFT: a) SGPT:

b) SGOT

c) PT:

d) Serum Albumin:

14.6) OGTT a) FBS :

b) 2 hr after 75 gm glucose:

14.7) HbA1C:

14.8) TSH

14.9) serum B12 assay:

14.10) CXR PA view

14.11) ECG

14.12) Echocardiography:

14.13) CSF Study:

14.14) NCS (Nerve conduction study):

15. Therapeutic Response:

Parameters	Assessment Before treatment (A 0) Date:	Assessment After 1 wk (A 1) Date:	Assessment After 6 wk (A 2) Date:	Assessment After 12 wk (A 3) Date:
A) Leg Swelling				
B) Muscle Power (MMRC grading) Upper Limb Lower Limb				
C) Deep Tendon Reflexes Upper Limb Lower Limb				
D) Squat Test				
E) Sensory impairment				
Pain				
touch				
position				
Vibration				
Tingling, Numbness				
Hyperesthesia (VAS score)				
F) Muscle cramp (VAS score)				
H) Overall Neuropathy Limitation Scale (ONLS)	Arm Score..... Leg Score..... Total:	Arm Score..... Leg Score..... Total:	Arm Score..... Leg Score..... Total:	Arm Score..... Leg Score..... Total:

[figure not shown]
Medical Research Council (MRC) Scale for Muscle Power

0	no muscle contraction visible
1	Flicker of contraction but no movement
2	Joint movement when effect of gravity eliminated
3	Movement against gravity but not against examiner's resistance
4	Movement against resistance but weaker than normal
5	Normal power

Muscle tested for Power

Upper limb	Lower limb
Shoulder abduction	Hip flexion
Shoulder adduction	Hip extension
Elbow flexion	Knee flexion
Elbow extension	Knee extension
Supination	Foot dorsiflexion

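### The legible CRF has no field for diuretics or neuropathic-pain and cramp drugs, so in this single-arm study relief from such a drug started or increased after baseline would be credited to thiamine on four secondary rows

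*Combined protocol and SAP*

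**What the plan says.** Section 5.1 describes a self-controlled "clinical trial (pretest – posttest design"), so there is no concurrent comparison group. The secondary outcomes in 5.11 are "Comparison and Assessment of clinical features at presentation and after treatment: leg swelling, muscle cramp, muscle power (MRC grading), deep tendon reflexes, sensory impairments", with the squat test.

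The entry risk factors in 5.6 end with "chronic. diuretics use, renal dialysis, total parenteral nutrition", and leg swelling is entry sign f. The only drug rule in 5.6 excludes neuropathy caused by drugs such as isoniazid or phenytoin. Section 8, point 4, says that patients will be treated according to the guideline for the disease.

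In the Part G case record form, the associated-conditions item reads "GIT surgery/ Chr. Diarrhoea/ Chr. Vomitting/Renal disease/ cancer/ pregnancy/others (specify"). Item 15 has columns for before treatment (A0) and for weeks 1, 6 and 12 (A1 to A3). Its rows include leg swelling, "Tingling, Numbness", "Hyperesthesia (VAS score") and muscle cramp (VAS).

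Section 5.10 assigns quantitative and multi-category variables to Friedman's test and yes/no variables to Cochran's Q. It has no rule for co-treatment. Section 5.12 defines a label by recovery: "Probable dry beriberi: Above symptoms recovered after thiamine treatment".

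**The concern.** With no control arm, every change from A0 is read as response to thiamine. Four item 15 rows can also respond to other common drugs. A diuretic can reduce leg swelling. A neuropathic-pain drug can reduce tingling and the hyperesthesia score. A cramp drug can reduce the cramp score. If one of these is started or increased after A0, the form as it reads gives no means of seeing it.

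Timing matters too. Drugs given on the ward may be partly traceable from hospital records. Changes made after discharge, up to weeks 6 and 12, probably could not be recovered later. The data have to be collected at the visits.

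The diuretic gap has a second side. Chronic diuretic use can qualify a patient for entry, and the Introduction names loop diuretics as a cause of thiamine loss, but the form does not ask about them by name even at baseline.

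**Working it through.** **1. Where a drug could be recorded.**
- Section 5.9 takes a history once, after consent.
- The associated-conditions item lists diseases and pregnancy. Its free-text option might catch a diuretic, once, at baseline.
- The examination and investigation items ask for no drugs.
- The legible rows of item 15 hold signs, VAS scores and ONLS only.

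So no legible item prompts for a drug, a dose or a change at A1, A2 or A3. Figures are missing from the form as supplied and the item 15 lettering passes from F to H, so this finding covers the legible text only.

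**2. Which outcomes are exposed.**
- *Exposed:* leg swelling; the tingling part of its row; hyperesthesia VAS; cramp VAS. The VAS key in Part G treats hyperesthesia and neuropathic pain as one scale, so this row is a pain score that a pain drug can lower.
- *Little exposed:* muscle power, reflexes, squat test and examined sensation.
- *Primary ONLS:* mostly function and gait, so exposed only indirectly. The clearest route is arm grade 1 (minor symptoms, no listed function affected) falling to 0, which is 1 point on a 0 to 12 scale.

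**3. Direction.** Starting or increasing a drug favours thiamine. A stable chronic diuretic produces no before-after change. Stopping or reducing a drug would tend to count against thiamine on the same row.

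**4. Planned test for each row.** Leg swelling is graded in four steps in the presenting-symptoms item, and hyperesthesia and cramp are VAS scores, so 5.10 sends these three to Friedman's test. Only the tingling row is plausibly yes/no and would go to Cochran's Q.

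**5. Size.** The plan's only related figure is the sample size in 5.7, with p = 0.8, d = 0.08 in the worked formula, N = 75 and z = 1.96:

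n = (1.96² × 0.8 × 0.2 × 75) / (0.08² × 74 + 1.96² × 0.8 × 0.2) = 46.10 / 1.088 = 42.4

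The plan prints 41.6 and uses 42. Then 42 × 1.3 = 54.6, which gives its 55. The 80% is a per-patient response rate ("from our experience, 80% of these patients show positive response"). The plan defines no response proportion for any single row, so it gives no target against which to size this bias.

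For illustration only, suppose a row were summarised as improved or not. Let p be the true thiamine response, c the share of thiamine non-responders given a relevant drug, and r the share of those who improve on it. The apparent response then rises by (1 − p) × c × r. None of the following values for c and r is in the documents.
- p = 0.8: from 0.2 × 0.10 × 0.30 = 0.6 points to 0.2 × 0.50 × 0.50 = 5 points.
- p = 0.6: from 0.4 × 0.10 × 0.30 = 1.2 points to 0.4 × 0.50 × 0.50 = 10 points.
- c = 0: no rise at all.

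On graded and VAS rows a co-drug could also deepen the improvement of a true responder, which this formula does not capture.

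**The case against.** The strongest reply is that the pathway is hypothetical. The documents do not say that any such drug is started or changed, and the primary outcome is hardly touched. That stands, and it limits the point to a minor one. It does not remove it: if no drug changes, two completed rows would show so.

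A second reply is that drug history is partly covered. Excluding drug-induced neuropathy requires asking about drugs, the history is recorded, and the schedule includes piloting and finalising the form. This is fair for baseline. It does not cover changes after A0.

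A third reply is that the uncontrolled design is the larger limitation, since natural recovery and diet change would remain even with perfect drug records. That is also true. Recording drugs closes one gap and does not isolate the thiamine effect.

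A reader might go further and infer that the efficacy conclusion is compromised, or that significant results would be false. The documents support neither. They give no co-drug use from which to calculate an effect on significance, and ONLS is largely a functional scale. Nor should a reader infer that the probable dry beriberi label is widely affected. It is most naturally read as requiring all presenting signs to recover, and no analysis of it is planned.

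**Conclusion.** The point holds as a minor one, and the remedy is a cheap improvement. The legible form does not record concomitant drugs at any of the four assessments, and the protocol does not restrict or stabilise diuretics or neuropathic-pain and cramp drugs. Before-after improvement in leg swelling, tingling, hyperesthesia VAS and cramp VAS could therefore include a drug effect that nobody could later separate out.

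This rests on two conditions: that such a drug is started or increased after A0 in some patients, which the documents do not state, and that no field was lost with the missing figures. The size cannot be derived from the documents and may be negligible; the ranges above are assumptions, not estimates.

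**What to change.** 1. Add two rows to CRF item 15 at A0 to A3: diuretic; neuropathic-pain or cramp drug. Code each as none, same, started or increased, or stopped or reduced, with the date. The A0 entry also documents the diuretic risk factor.
2. In 5.10, report how many patients fall in each category for each drug type.
3. Keep all planned outcomes and analyses, for all patients. No treatment needs to be prohibited.
4. If any relevant drug was started or increased, add one sensitivity analysis of the four rows, labelled as conservative. Improvement on the affected row after the drug change is not counted: carry the last value before the change, unless the observed value is worse. Use the planned test for each row: Friedman for graded and VAS rows, Cochran's Q only for a row recorded as yes/no.

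The cost is slight extra recording at existing visits and a few sentences in 5.10; the sample size does not change. The downside is that some true thiamine responders will count as non-responders in the sensitivity analysis. This is sharpest when a drug is started in the first week, because A0 is then the last usable value. The result should be presented as a bound for this one problem.

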areas and gradually expanding. The sensory effects are usually symmetrical although the side that is greater use tends to be affected first. Paraesthesia is often the earliest sign of diminished sensitivity and the patients complains of burning sensation in the legs and toes. Although rare, sensory disturbances of the oral cavity are encountered in a few cases. Paralysis of the motor nerves occurs after the sensory disturbances. This also begins in the tips of the lower extremities, then in the fingers, and ascends progressively. There is increasing muscular weakness which is readily demonstrated by the inability of the individual to rise from a squatting position without assistance and, as the disease progresses, there is atrophy of the leg muscles. The tendon reflexes are also affected especially with loss of ankle and knee jerks. Painful calf muscles and, eventually, foot drop and, later, wrist drop may also develop. Advanced neurological changes may result in great difficulty in walking and may even lead to complete paralysis. Frequently, vertigo and instability of the body during walking are noted in beriberi patients. The shaky gait is equivalent to positive Romberg's sign and mostly caused by impaired vestibular function in advanced cases although it is partially due to decrease deep sensations. Nystagmus, as a sign of manifestation of vestibular malfunction, has been reported to occur particularly in alcoholics who developed Wernick's encephalopathy.^{1,6}

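### Two of the six sensory before/after outcomes, burning and tingling, cannot be derived as listed: the case record form names no field for burning and records tingling only together with numbness.

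*Combined protocol and SAP*

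**What the plan says.** Section 5.11 gives as its secondary outcome a comparison of clinical features at presentation and after treatment. The sensory part of that list is "sensory impairments (tingling /burning /pain/ touch/ position /vibration), squat test", where the squat test is a separate item. That makes six sensory components.

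The entry criteria in section 5.6, repeated in section 5.12, use the same features. One sign covers symptoms: "b) Positive sensory symptoms (burning, tingling or pain". The next covers examination findings: "c) Objective sensory deficit (pain, touch, position, vibration sense". The Introduction describes burning as an early complaint: "the patients complains of burning sensation in the legs and toes".

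The CRF has these sensory items:

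- Item 12.3, at baseline: "12.3) Sensory Impairment (pain, tingling, numbness): yes/ no".
- Item 12.6, at baseline, free text: "12.6) other symptoms (specify): Duration: Days".
- Item 13.7, at baseline: pain, touch, temperature, position and vibration, each coded 0, 1 or 2 for normal, diminished or absent.
- The first of the two items numbered 13.8, at baseline: "13.8) neuropathic Pain (VAS Score"), graded 0 to 3.
- Item 15, block E, at baseline and after 1, 6 and 12 weeks (A0 to A3): rows for pain, touch, position, vibration, "Tingling, Numbness", and hyperesthesia by VAS.

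Section 5.10 plans Cochran's Q test for dichotomous variables and Friedman's test for the others. Section 5.12 defines probable dry beriberi by recovery of the listed signs after thiamine.

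**The concern.** Specific objective 3 is to compare neurological features before and after treatment. Both planned tests need the same defined variable at every visit. A feature that the form does not name, or names only jointly with another, does not give such a variable.

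The classification of probable dry beriberi is also affected, because it asks whether the entry signs recovered. For a patient whose sign b was burning, the form has no named place to show whether the burning went away. Symptoms not recorded at a visit cannot be reliably reconstructed later.

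**Working it through.** No power or sample-size figure is involved. The check matches each sensory component in section 5.11 to the CRF.

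| Outcome in 5.11 | Entry sign | Baseline items | Row in item 15 (A0 to A3) | Derivable as listed? |
|---|---|---|---|---|
| Burning | b | none named | none named | No |
| Tingling | b | 12.3, with pain and numbness | joint with numbness | Not separately |
| Pain | b (symptom), c (sensation) | 12.3 and 13.8 (symptom), 13.7 (sensation) | pain row; hyperesthesia VAS row | Probably; label ambiguous |
| Touch | c | 13.7 | own row | Yes |
| Position | c | 13.7 | own row | Yes |
| Vibration | c | 13.7 | own row | Yes |

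Count: 1 (burning) + 1 (tingling) = 2 of 6 not derivable as listed; 1 of 6 ambiguous in label; 3 of 6 sound; 2 + 1 + 3 = 6.

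**Burning.** It is named in sections 5.6, 5.11 and 5.12, but not in items 12.3, 13.7, 13.8 or 15, nor in the VAS legend. Named fields: 0 at each of the 4 assessments.

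**Tingling.** Take a patient with tingling and numbness at A0 who at A3 has numbness only. If the joint row holds a single yes/no, it reads yes at both visits and shows no change, although the listed outcome resolved. Conversely, a patient with numbness alone at A0 and neither at A3 goes from yes to no, which would count as improvement in a symptom that was never present. The form prints no code for this row, so a careful assessor could write in both symptoms, but nothing tells assessors to do so.

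**Pain.** The word is a symptom in sign b and items 12.3 and 13.8, and a tested sensation in sign c and item 13.7. Two features of the form point to a reading. The VAS legend after the muscle list covers neuropathic pain and hyperesthesia on one scale, with the same 0 to 3 grades as item 13.8, so the hyperesthesia VAS row is the natural follow-up of that item. The pain row then opens the sequence pain, touch, position, vibration, which is the order of sign c and, apart from temperature, of item 13.7. Most likely, then, the pain row means pain sensation. The block heading does not settle it, because items 12.3 and 13.7 are both titled sensory impairment.

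**Entry sign b.** Item 12.3 can be answered yes on numbness alone, which is not part of sign b, and it does not name burning. It therefore cannot by itself confirm sign b. A nonzero grade in item 13.8 can confirm it through pain.

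**The case against.** The strongest case on the other side is that this is a labelling matter on a form that was still to be settled, since the time schedule includes piloting and finalization of the CRF. Burning could be written into item 12.6 or scored on the VAS for neuropathic pain and hyperesthesia. The joint tingling row has blank cells, so both symptoms could be entered. Section 5.11 numbers only one secondary outcome, of which burning is a small component.

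Part of this stands. Separate recording of tingling and numbness is possible, and burning may have been meant to fall under the VAS. But no document says so, item 12.6 has no counterpart at follow-up, and a single VAS grade could not separate burning from other pain. A finalization step is where to make the change; it does not make it.

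Three stronger readings are tempting, and the documents do not support them:

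- A reader might infer that the sensory outcomes as a whole cannot be derived. Touch, position and vibration each have their own row at all four assessments.
- A reader might infer that pain is lost too, because returning sensation and new pain would move one row in opposite directions. The VAS legend and the order of the rows make that reading unlikely. Pain and tingling are also in separate rows.
- A reader might infer that entry by sign b can never be verified. Item 13.8 documents symptomatic pain, and entry needs any two of six signs plus a risk factor. The gap concerns only patients without pain for whom sign b was decisive; the documents do not allow their number to be estimated.

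**Conclusion.** The point holds for 2 of the 6 sensory outcomes. Burning has no named field at any of the four assessments, and tingling is recorded only jointly with numbness. Their before/after change cannot be derived as listed, nor can recovery of sign b where it rested on either symptom. For pain, the label needs clarifying; the outcome is not shown to be missing. The primary outcome has a complete row of its own and is untouched, so this is a correction the plan should make, not a threat to its main result.

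The conclusion rests on the public text of the CRF. The lettering in item 15 passes from F to H and some figures are not shown, so a lost row cannot be fully excluded. The sensory rows sit under E, however, and item 12.3, which is intact, also omits burning.

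**What to change.** Change the CRF before it is finalized:

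- In item 15, add a burning row, and replace the joint row by one for tingling and one for numbness, each with a stated code at A0 to A3.
- Relabel the pain row as pain (pin-prick) sensation, coded 0/1/2 as in item 13.7, and the VAS row as covering neuropathic pain and hyperesthesia together.
- In item 12.3, record burning, tingling, pain and numbness as four separate ticks.
- In section 5.10, state that positive symptoms and sensory loss are analysed as separate outcomes.

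The cost is slightly longer form completion at each visit. No new procedure is needed: the change only adds or separates symptom entries in an assessment already planned for each visit.
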